#### *Sources of Materials*

Data will be obtained directly from participants, including: survey data, neuropsychological data, and health information. Data will also be collected from FSU SeniorHealth EHRs, but will only include the minimum PHI necessary to complete the proposed study. Data from the EHR will include the following information only from appointments pertinent to the study: patients' problem/diagnostic list, medication list, patient vitals, potassium levels, metabolic panels, HbA1C, CRP, scores on recent cognitive and psychological assessments (i.e., MoCA, depression inventories), and relevant provider notes about a patient's cognitive functioning. Finally, we will complete semi-structured interviews with the clinic providers and patient participants to assess implementation barriers and facilitators. Provider participants will also complete quantitative measures on implementation acceptability (i.e., Modified version of the Assessment of Fit Scale for outpatient clinics). Only [name] and key study personnel will have access to individually identifiable private information (e.g., names, dates of birth, etc.) outside of clinic staff. Staff responses will not be shared with other providers at the clinic. All the information extracted from EHR will be saved on FSU's W drive until it is deidentified. Deidentified information will be stored in locked file cabinets, within a locked suite, and transferred to a password protected computer once coded.

## 7.0 Data and Specimen Banking\*

Blood samples will be collected by a certified medial assistant in a phlebotomy lab at the Center for Translational Behavioral Science. Samples will be labeled and identified only by an ID number. These samples will be used to assess comprehensive metabolic profiles (CMPs) and HbA1c of participants. Samples will be stored temporarily in a -80 F freezer in the phlebotomy lab. HbA1C will be extracted through point-of-care and analyzed immediately. CMPs will be analyzed using a Piccolo Xpress Chemistry analyzer in the College of Human Sciences with the assistance of [name] and [name]. Samples will be transported in a medical transport cooler by trained research personnel. Once results of the CMPs are returned, these will be coded and stored with other participant data (described below). Biological samples will be disposed of after analysis as biowaste.

### **Data for Future Use**

Participants consent to these procedures as part of the consent process.

Data collected during this research study may be used for future research purposes. The data stored will be de-identified. De-identified Data that cannot be linked to participants will be kept indefinitely; this data will be saved for future use and may be shared with other researchers. This data may be used for secondary data analysis to inform future publications examining late-life health and cognition, as well as preliminary data for future grant applications.

At the end of the study data collected may be made available, in accordance with the NIH Data Sharing Policy ([http://grants.nih.gov/grants/policy/data\\_sharing](http://grants.nih.gov/grants/policy/data_sharing)). This data will be saved for future use and may be shared with other researchers. By participating in this study, participants are agreeing to allow us to save and share their data anonymously for research purposes.

We will ask consented participants if they wish to be contacted for future research opportunities. On the Study consent form, we ask participants if they wish to be contacted about future research opportunities in which they might be eligible. For this study, information retained for individuals that give permission to keep their contact information for future research opportunities will include: Names, Email addresses and Working phone number. This information will be collected using a secure REDCap form, only accessible by the study team. Contact information will be stored and maintained in a password protected excel file, and will be kept separate from individual study related information. Access to this information will be limited to only designated study team members throughout the duration of the study.

After consenting to participate in this study, individuals interested in being contacted for future studies will be directed to a secure REDCap form to provide their permission to be contacted, contact information (email and phone) and age. The statement on the Consent form is as follows:

**Date and time**

All screened individuals will be asked if they are interested in being contacted about future research studies. Only by answering "Yes" to interested in future research studies, they will be asked by the study team member conducting the screener to provide their contact information (email and phone) and age. The statement on the Study Screener form is as follows: "Would you like to be contacted for future studies?"

The study team will carefully review and document which participants granted permission for the study team to retain their information. Participants who say "yes" will have their information stored in a password-protected file, separate from the study data, and accessible to only trained members of the study team. Participants may request to be removed from the mailing list at any time, in which case a note will be made for data cleaning to remove that individual when data is cleaned.

#### *Sharing of Results with Subjects\**

Participants will not receive diagnostic feedback about their performance on the phone cognitive assessments or results of any biological or emotional testing. Participants may of course request to view their own medical records through the FSU SeniorHealth Clinic as part of their usual care; however, the study team will not release individual results of testing to participants through the study.

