## **13.0 Withdrawal of Subjects\***

A participant meets the criteria for “premature discontinuation” if they withdraw from the study before completion. Premature discontinuation would include participants who decide to voluntarily end their participation early for any reason, as well as participants who may be withdrawn from the study based on an adverse response to the intervention and consultation with the MD, [name]. Participants may choose not to attend some sessions or complete all assessments, but they will not be compensated for assessments they do not complete. Participants will not be involuntarily removed from the study for missing sessions or assessments if they indicate that they would like to remain in the study. If a participant fails to attend 2 consecutive appointments and assessments without notifying the study team, we will reach out to them up to 3 times via phone and/or email to assess their interest in continuing in the study. No response from the participant will be considered a premature discontinuation, and they will be withdrawn from the study. Completion represents completing the assessments in addition to the intervention. There are no alternative treatments or procedures for participants that choose to withdraw from the study, other than care as usual. Participants will be reminded that their participation is voluntary and they may choose to end participation in the study at any time.

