## **14.0 Risks to Subjects\***

We are only recruiting individuals without unstable chronic medical conditions for this nutrition intervention (e.g., significant gallbladder problems, cancer, Type 1 diabetes). Further, participants who are underweight based on BMI will be excluded ( $BMI < 19$ ). Individuals with these conditions will be screened out in the initial call prior to completing the consent process.

Thus, primary risks associated with changing diet may include, gastrointestinal upset (i.e., bloating, diarrhea, gas, and constipation), change in weight, headache, and fatigue. Participants will be closely monitored by the study team on a weekly basis to assess any adverse response to the diet. If a significant adverse response is reported or identified, the team will consult the MD consultant on the team, [name], for a clinical decision.

Participants will be asked to provide two fasting blood samples for assessment of metabolic panels and HbA1c. There may be slight discomfort when inserting the needle. Even with precautions, minor bruising and swelling around the puncture site can occur. Because every person’s veins are different, and veins move frequently, bruising can occur even with the most experienced phlebotomists. Participants will be required to fast for 8-12 hours prior to the blood draw. The primary risks associated with fasting may include lightheadedness. Thus, we will provide snacks for participants after the blood draw is complete.

Other risks include mental fatigue from completing some potentially challenging cognitive tasks.

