### **Protection against Risk**

Participants will be given the option to end participation at any time with no penalty for doing so. Participants may take breaks from testing as requested or choose not to answer sensitive questions.

For the intervention portion, participants will be closely monitored by the group leaders on a weekly basis to assess any adverse response to the diet. If a significant adverse response is reported or identified, the team will consult the MD and nurse practitioner on the team for a clinical decision.

Physical copies of all tests and measures will be stored in locked cabinets in a secured suite in Research Building B at Innovation Park or maintained in the SeniorHealth clinic (for SeniorHealth patients only). Data from these physical copies will be coded and transferred to electronic spreadsheets, which will be password protected and stored in encrypted locations. All identifiable participant data will be stored separately in a password protected document. Data will be connected to an ID number rather than participant information.

Prior to the blood draw CMAs will wash and sanitize hands then don gloves. Gloves will stay on for the duration of the blood draw. Once the blood draw is complete the needed will be capped and disposed of in the appropriate sharps container. CMAs will keep gloves on until the draw area is sanitized and disinfected. After the area has been cleaned appropriately, CMAs will doff gloves, dispose of them in a biohazard bag and wash hands. Biological samples will be stored in a -80 F freezer in a locked phlebotomy lab at the Center for Translational Behavioral Sciences. Only the study PI and CMAs on the team will have access to this laboratory. Samples will be disposed of as biowaste after analysis.

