### **15.0 Potential Benefits to Subjects\***

A goal of the current study is to assess whether ketogenic nutrition may be beneficial for memory and pain severity in older adults and whether the use of an MI-CBT group approach may improve adherence to this type of nutrition. Previous research has demonstrated that a low-carbohydrate diet has multiple benefits on cognitive functioning, pain, and other health factors in older individuals. Thus, participants will be provided with a supportive environment for making this diet change as well as empirically validated cognitive behavioral skills for behavior change in general.

During the proof-of-concept preliminary trial, participants reported improvements in energy stability, alertness, blood glucose levels, and mood. Participants may experience improvements in their cognitive status and will be closely monitored by health professionals.

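### The ban on giving participants any test result has no exception, and the stated route to the study MD does not reach an abnormal Time 1 metabolic panel or HbA1c

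*Protocol*

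**What the plan says.** Sharing of Results with Subjects says that participants will not be given "results of any biological or emotional testing", and closes with the rule that "the study team will not release individual results of testing to participants through the study". The one access it mentions is a participant's own SeniorHealth clinic record, viewed as part of usual care.

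Section 6.0 takes a fasting metabolic panel and HbA1c at Time 1 (baseline) and a second fasting draw at Time 2, in the final weeks of the programme. Section 7.0 sets out the handling. For HbA1c: "HbA1C will be extracted through point-of-care and analyzed immediately". For the panel: "Once results of the CMPs are returned, these will be coded and stored with other participant data".

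Clinical oversight is described in four places:

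- Section 14.0: "Participants will be closely monitored by the study team on a weekly basis to assess any adverse response to the diet", with the MD consulted if a significant adverse response is reported or identified.
- Protection against Risk, within Section 14.0: "For the intervention portion, participants will be closely monitored by the group leaders on a weekly basis", again to look for an adverse response to the diet, with the MD and nurse practitioner consulted.
- Section 13.0: a participant may be "withdrawn from the study based on an adverse response to the intervention and consultation with the MD".
- Section 15.0, in general terms: participants "will be closely monitored by health professionals".

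**The concern.** The study measures blood chemistry and HbA1c in people aged 60 to 85 shortly before asking them to change their diet substantially. Section 5.0 sets net carbohydrate at 125 g in week 1, 75 g in week 2 and 50 g or less in week 3, then 20 g or less in weeks 5 and 6, depending on ketone level and macronutrients. The Time 1 draw can therefore show, before that change, something a clinician would want to act on.

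Read as written, the protocol has two effects at that moment. Staff may not tell the participant the result, whatever it is. And no instruction sends the result to the MD, because the stated trigger is a response to a diet that has not begun. A clearly abnormal value could be filed as data while the participant starts the programme without knowing of it. What is at stake is participant safety, not the validity of the comparison.

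**Working it through.** The protocol gives no figure to reproduce, so the check sets its provisions side by side.

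**1. Is the bar on disclosure qualified?** No. It covers any biological or emotional test result and is then restated for all individual results. The clause on clinic records is not an exception: it concerns usual-care records, nothing says that study results are entered there, and it gives a participant from outside the clinic no route.

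**2. Does the bar stop staff from telling the MD?** No. It governs release to participants. Internal escalation is neither forbidden nor instructed.

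**3. Does the MD route reach a Time 1 result?**

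| Provision | Trigger | Reaches an abnormal Time 1 panel or HbA1c? |
|---|---|---|
| Section 14.0, weekly monitoring | Adverse response to the diet | No: the diet has not started |
| Protection against Risk | The same, within the intervention portion | No: Time 1 comes before that portion |
| Section 13.0, withdrawal | Adverse response to the intervention | No, for the same reason |
| Section 15.0, general statement | None given | Not determinable: no reader, trigger or action |
| Section 17.0, monitoring plan | Identifiers, data access, database security, confidentiality | No: clinical results are not listed |

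Time 2 differs. It falls within the programme, so an abnormal result could be treated as an identified adverse response. No one is named to look at it, however.

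**4. Does screening close the gap?** It depends on where the participant comes from.

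- *Clinic patients.* At Time 0 (Section 6.0) the team extracts metabolic panels, HbA1c and potassium from the health record and uses the record for a secondary eligibility screen. Earlier laboratory values are thus considered before the diet, although the study's own Time 1 draw is not named in that step.
- *Non-clinic recruits.* Section 6.0 accepts self-reported conditions and medications. The screening-call paragraph provides a physician safety review that includes these participants, but on self-report or supplied records. Section 12.0 makes supplying records and recent laboratory work optional and lets the study team settle eligibility on self-report. For someone who supplies nothing, the Time 1 draw may be the only recent laboratory data the study holds.

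**5. Can the result be acted on in time?** HbA1c is read at the point of care, so its value is known at once. The panel is stored frozen, transported and run on an analyser in another college, with no turnaround stated. The timeline in Section 8.0, as its table reads, puts baseline assessment for groups 1 and 2 in months 2 and 3 and their intervention in months 3 and 4, so the interval may be short for some.

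**6. How many results would the MD see?** Maximum enrolment is 60 (Section 11.0). With one panel and one HbA1c per draw and two draws each, that is at most 60 × 2 = 120 sets of results, of which 60 are from Time 1.

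**The case against.** The strongest reply is that much of this is silence rather than error. The consent pages are not available and could contain a provision for abnormal results. Nothing stops the team from showing a bad panel to the MD, excluding or withdrawing the participant, or giving clinical advice. The KNA groups are co-led by a clinical psychologist and a nurse practitioner, and the KN-only groups are led by a nurse practitioner. The exclusions do not rest wholly on self-report: low BMI and major neurocognitive disorder also exclude, and records are checked where they exist. Carbohydrate is reduced in steps to limit adverse responses.

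Most of this stands, and it limits the point. A reader might infer that the protocol leaves abnormal results without any clinical oversight, or forbids staff to act on them. The text supports neither reading. A reader might also infer that a worrying PHQ-9 would go unheeded. The weekly PHQ-9 could feed the weekly monitoring by clinician group leaders, and detailed routing of questionnaire scores is an operating matter that may be written elsewhere. The documents do not establish a failure there.

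The reply does not remove the explicit rule. A consent-form provision, if there is one, would conflict with protocol text that bars release without exception, and the protocol would still need to match it. Nor does it alter the trigger in Sections 13.0 and 14.0, which a pre-diet result cannot meet.

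**Conclusion.** The point holds as a minor safety correction. The disclosure bar is absolute, and the stated MD route does not extend to a laboratory abnormality found at Time 1. The exposure lies mainly with non-clinic recruits who supply no records.

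Its size cannot be computed: the protocol gives neither a rate of abnormal panels or HbA1c values nor the share of participants recruited outside the clinic. Counting visits or tests would not measure the risk.

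It might be inferred that the gap distorts the comparison between KNA and KN-only. It does not: the rule applies to both arms alike, and Time 1 results are handled in the same way in each.

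The conclusion assumes that Time 1 comes before carbohydrate reduction, as its description as the baseline assessment implies, and that no separate operating procedure already sends Time 1 results to the MD.

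**What to change.** 1. **Sharing of Results with Subjects.** Add an exception to the bar: findings that the study MD judges clinically important will be communicated to the participant or, with permission, to the participant's own physician.
2. **Section 7.0.** State that the MD already on the team sees the point-of-care Time 1 HbA1c, and the Time 1 panel where it can be run in time, before carbohydrate reduction begins, and sees the Time 2 results when they are returned.

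The wording is short and no new staff are needed, but there is a cost. Panels are stored and transported before analysis and groups have set start dates, so getting Time 1 panels read before week 1 takes some scheduling effort. The qualifier on the panel allows for that, at the price of leaving some panels unread at the start. Results can be traced to a person, because Section 18.0 keeps the linking file until that participant's data collection is complete.

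HbA1c and the metabolic panel are also outcomes under Objective 2. A few participants may learn such a value and change their behaviour. Each disclosure should therefore be recorded, with its date and the arm, so that it can be taken into account when the outcomes are described.

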## **8.0 Study Timelines\***

See table below.

Timeline for proposed research activities		1	2	3	4	5	6	7	8	9	10	11	12
Year 1													
Submit IRB application		X											
Refining implementation with key stakeholders			X	X	X								
Cleaning and standardizing the EHR				X	X								
Training workshop for clinic staff					X								
Standardize clinic procedures for screening			X	X	X	X	X	X					
Initial screening and recruitment (build waitlist)							X	X	X	X	X	X	X
Resubmit K23 application										X	X		
Recruitment calls											X		
Year 2		1	2	3	4	5	6	7	8	9	10	11	12
Pre-intervention EHR data extraction (groups 1&2; T0)		X											
Baseline phone assessments: groups 1&2 (T1)			X	X									
Intervention period				X	X								
Post-intervention phone assessments (T2)					X								
Post-intervention EHR data extraction (T3)						X	X	X					
Pre-intervention EHR data extraction (groups 3&4; T0)						X							
Baseline phone assessments: groups 3&4 (T1)						X	X						
Intervention period							X	X					
Post-intervention phone assessments (T2)								X					
Post-intervention EHR data extraction (T3)								X	X	X			
Data cleaning and Manuscript development			X	X	X	X	X	X	X	X			
Develop and submit new NIA application					X	X	X	X	X	X	X		

## 9.0 Inclusion and Exclusion Criteria\*

### Study Population

Older adults, between the ages of 60-85, and with possible or pre-mild cognitive impairment (MCI) were chosen in order to specifically assess the effect of the intervention on individuals at higher risk for converting to AD. These individuals may observe the greatest cognitive benefits from the intervention, while not requiring a caregiver or significant other to provide assistance or consent. The ages 60-85 were chosen, as this age range is often where early signs of dementia begin to emerge on neuropsychological testing.

### Inclusion Criteria

To meet eligibility for inclusion in the intervention, participants must be 60-85, meet criteria for possible mild cognitive impairment, have a Telephone MoCA score >12, be English speaking, and have internet access with video conferencing, and report interest in participating in a nutrition intervention. In addition to the criteria above, a subsample of 20 participants will be selected based on self-reported pain on the Rolland-Morris pain scale (A1) of 3 or greater during the past week.

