## 1.0 Study Summary

Study Title	Pilot Trial of a Motivational Interviewing and Cognitive Behavioral Therapy (MI-CBT) Ketogenic Nutrition Adherence Program for Older Adults
Study Design	Block Randomized Pilot Pragmatic Clinical trial completed virtually through HIPAA Compliant Zoom
Primary Objective	Assess feasibility and acceptability of all protocol components of a pilot pseudo-pragmatic trial testing a 6-week telehealth KNA program compared to a KN information only group for older adults with MCI in the FSU SeniorHealth clinic to prepare for a full-scale trial.
Secondary Objective(s)	Assess signal of initial effect of the KNA program on important clinical outcomes and adherence relative to a KN information-only condition.
Research Intervention(s)/Investigational Agent(s)	Using a centralized telehealth approach, the KNA program will consist of 6 weekly group meetings, which will take place via HIPAA-compliant Zoom. The group will be co-led by a clinical psychologist and a nurse practitioner with expertise in nutrition. Approximately half of each session will be devoted to providing nutrition information and half devoted to psychoeducation, MI activities, and CBT skills. Participants assigned to the KN-only group will also attend weekly group meetings with information about how to adhere to KN and how to track macronutrients, food intake, and ketone levels. Participants will be provided with the same participant binder as the KNA group with informational handouts and KN recipes, but without the MI-CBT handouts. Participants will be asked to track their food intake and daily ketone levels, and will be provided with the option of attending a weekly Zoom meeting where they may ask questions about KN and receive additional nutrition information as needed. These optional meetings will be offered for 6 weeks.
IND/IDE #	
Study Population	Older adults 60+
Sample Size	N = 60
Study Duration for individual participants	1 year, including pre/post assessments; intervention is 6 weeks.
Study Specific Abbreviations/Definitions	KN = ketogenic nutrition; KNA = ketogenic nutrition adherence; MCI = Mild Cognitive Impairment; PCT = Pragmatic clinical trial

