## 2.0 Objectives\*

- **Objective 1:**

Assess feasibility and acceptability of all protocol components of a pilot pragmatic trial testing a 6-week telehealth KNA program compared to a KN information only group for older adults with possible or pre-MCI in the community and at a senior health clinic to prepare for a full-scale trial.

Specifically, we will examine the feasibility of the recruitment, retention, assessment, electronic health record (EHR) downloads, and intervention delivery methods through the FSU SeniorHealth™ clinic. If we determine it is not feasible to recruit the full sample through this clinic, we will expand recruitment to the community.

We hypothesize that

- *The study protocol (MI-CBT KNA program) will result in high patient retention (90%) and patient attendance of intervention sessions (80%), and*
- *A centralized MI-CBT telehealth delivery approach will be associated with high intervention acceptability ratings from patients and key stakeholders.*
- *MI-CBT KNA program will result in higher adherence to KN compared to the KN information-only group as evidenced by higher levels of ketones at week 6 of the intervention using at-home ketone urinalysis test strips.*

To test these hypotheses, we will use a mixed methods approach using qualitative interviews, quantitative measures of patient satisfaction with the intervention (using the Client Satisfaction Questionnaire) and provider perception of the overall fit of the intervention in the clinic, and of patient intervention attendance and study attrition. Qualitative data from providers and patients will be thematically coded to further examine acceptability and barriers to implementation.

- **Objective 2:**

Assess signal of initial effect of the KNA program on important clinical outcomes and adherence relative to a KN information-only condition.

We hypothesize that *patients in the KNA condition, relative to the KN-only condition, will show 1) higher rates of clinically significant improvements on the RBANS total scale scores, improvements in daily functioning (FSQ), decreases in patient CAIDE risk score, improvements in HbA1C levels and comprehensive metabolic panels, and improvements in self-reported pain using the Rolland-Morris Pain scale, and 2) improved adherence to KN, as evidenced by higher levels of measurable urine ketones in the KNA condition compared to the KN-only condition.*

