#### **4.0 Study Endpoints\***

This study will focus on assessing the feasibility and acceptability of all protocol components of a pilot pragmatic trial, testing a 6-week telehealth KNA program compared to a KN information only group for older adults with possible MCI in the community and at a senior health clinic to prepare for a full-scale trial. We will use a mixed methods approach using qualitative interviews, quantitative measures of provider's perception of the overall fit of the intervention in the clinic, and of patient intervention attendance and study attrition. Qualitative data from providers and patients will be thematically coded to further examine acceptability and barriers to implementation.

We will also focus on assessing signal of initial effect of the KNA program on important clinical outcomes and adherence relative to a KN information-only condition. Data on clinical outcomes will be extracted or requested from patient health records before and after engaging in the intervention and to compare group differences. Patient participants will also complete assessments in-person, following appropriate COVID-19 precautions, pre- and post-intervention.

We expect that patients in the KNA condition will have higher rates of transferring to the normal range on the RBANS, greater improvements in functional status on the FSQ, and greater improvements in self-reported pain and other health indices. Additionally, we expect higher rates of measurable ketones (trace or higher) in the KNA program compared to KN-only based on daily, at-home urinalysis test strips. Combined, these data will provide important information about the clinical effects of the programs and feasibility of the proposed study components for a larger PCT.

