Preliminary screen. After confirming interest in being contacted about the study, participants will be contacted by a member of the research team and screened for eligibility. This screening will include a telephone MoCA, sections 1 and 4 from the Functional Status Questionnaire, a brief memory complaint scale, self-rated pain during the past week (0-10), and self-reported height, weight, and age. Participants will also be asked to report any restrictive dietary or medical conditions that may make them unable to change their nutrition. Participants will be compensated with a \$5 e-gift card for completing the screening and will be asked to provide their full name and email address to receive the gift card. This contact information will not be retained for future research purposes. All screened participants will be provided with a handout on healthy living designed in collaboration with the SeniorHealth physicians. If participants are eligible, then they will be sent an online consent form, which they will read and review using HIPPA-compliant Zoom with a member of the research team before signing. For participants who are patients at FSU SeniorHealth, the study team will then complete a final eligibility check of the patient's EHR and review with the physician to confirm eligibility and ensure participant safety. For participants who are not patients at FSU SeniorHealth, we will request patients provide a copy of their most recent medical records, including health conditions, medications, and recent lab work – this step will be optional. The study team will determine final eligibility of these patients based on self-reported health conditions or review of the records they provide. Participants who are eligible and consent to participate will have screening data linked with other study data, in order to reduce redundancy in assessment measures. Patients and participants who have previously provided consent to be contacted for research may be called or emailed to assess interest in the study if they are not screened during their normal clinic visits. From this sample, we will recruit up to 60 patients who meet criteria for possible MCI (e.g., MoCA score of 18-25 and some self- or other-reported changes in daily living due to cognition). 20 participants will be selected based on self-reported pain of moderate intensity or greater in addition to the other inclusion criteria. There will be two intervention conditions: 30 patients will be randomly assigned to the 6-week KNA group program and 30 to the KN-only condition. All patients will be given the option of signing up for one of three start dates for the programs, with 10 patients maximum in each group. These conditions are designed to determine whether MI- CBT strategies improve adherence to KN, thereby enhancing the benefits compared to providing KN information alone. Key stakeholders in the clinic will be engaged early in the project to increase buy-in to the intervention and to introduce staff to the project.

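### Do the differing labels for the study population (MCI, possible or pre-MCI, possible MCI) leave part of the primary objective without an entry route?

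*Protocol*

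**What the plan says.** Six places state whom the study addresses or admits.

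- Section 1.0, Primary Objective: "older adults with MCI in the FSU SeniorHealth clinic to prepare for a full-scale trial".
- Section 2.0, Objective 1: "older adults with possible or pre-MCI in the community and at a senior health clinic".
- Section 4.0, Study Endpoints: "older adults with possible MCI in the community and at a senior health clinic".
- Section 9.0, Study Population: older adults "between the ages of 60-85, and with possible or pre-mild cognitive impairment (MCI) were chosen".
- Section 9.0, Inclusion Criteria: "participants must be 60-85, meet criteria for possible mild cognitive impairment, have a Telephone MoCA score >12".
- Section 12.0, Preliminary screen: "From this sample, we will recruit up to 60 patients who meet criteria for possible MCI", followed by "30 patients will be randomly assigned to the 6-week KNA group program and 30 to the KN-only condition".

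Section 12.0 also describes possible MCI, by way of example, as a MoCA score of 18 to 25 together with some change in daily living, reported by the participant or by someone else and due to cognition. Pre-MCI is not described anywhere. Objective 1 makes recruitment one of the things to be assessed: "we will examine the feasibility of the recruitment, retention, assessment".

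**The concern.** A pilot's recruitment and retention figures describe a population, and the full-scale trial will be planned from them. If the objective names a group that the entry criteria turn away, the study cannot deliver what it promises for that group, and people it meant to include would be logged as ineligible.

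Read quickly, the protocol does this. Objective 1 and the Study Population paragraph join possible and pre-MCI with *or*, which suggests two groups. The Inclusion Criteria, in the same Section 9.0, then require possible MCI. Section 12.0 fills every place from people who meet that description. The Study Summary uses a third term, MCI. The stake would be the meaning of the feasibility result; no statistical test is affected.

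**Working it through.** The check is mainly a comparison of text, and the protocol gives no figure to reproduce.

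**1. Count the labels.** MCI: 1 place (Section 1.0). Possible or pre-MCI: 2 places (Sections 2.0 and 9.0, Study Population). Possible MCI: 3 places (Sections 4.0, 9.0 Inclusion Criteria, and 12.0). That is 1 + 2 + 3 = 6 places and three labels, so the inconsistency in wording is real.

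**2. Separate the places that decide who enters from those that describe.** Only the Inclusion Criteria and Section 12.0 decide admission. Both say possible MCI, so someone screening participants gets one answer from them.

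**3. Test whether any place is closed to pre-MCI.** The full allocation is 30 + 30 = 60, all for possible MCI, which suggests 60 − 60 = 0 places for pre-MCI, or 40 − 40 = 0 at the minimum enrolment in Section 11.0. The subtraction assumes that nobody with possible MCI could also be called pre-MCI. If *k* of those enrolled fit both descriptions, the number is *k*, and the text allows any value from 0 to 60 (0 to 40 at the minimum). The zero comes from the assumption and not from the protocol.

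**4. Test that assumption against the text.**
- Pre-MCI has no definition, so nothing sets it apart from possible MCI.
- Section 10.0 describes MCI as a slight decline that calls for compensatory strategies. That is a description of MCI itself, not of possible MCI.
- The Section 12.0 description asks for a screening score and some reported change. A person with mild reported change who does not yet need compensatory strategies could meet it while falling short of MCI in Section 10.0. The two sections therefore leave room for overlap.
- The Section 12.0 description is given as an example, and the Inclusion Criteria set a lower MoCA limit but no upper one. Neither shuts out a milder case.

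**5. Check that the two MoCA statements can be applied together.** Every score from 18 to 25 is above 12. The Exclusion Criteria tie the lower limit to capacity to consent, so it is a separate floor. The telephone form is the one used in the same screening call and is the natural reading of the 18 to 25 range.

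**6. Check what the objective promises.** Objective 1 names a single combined population. It does not promise a separate feasibility result for pre-MCI.

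**The case for a change.** The best argument for a change is that *or* normally separates alternatives, that a stage before MCI would not obviously come with reported change in daily living, and that one sentence would have settled the matter if the terms were meant as synonyms. Without that sentence, admission of a borderline person may depend on who does the screening. Entry criteria also belong in the protocol, so the point cannot be left to a statistical analysis plan.

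Part of this stands. The labels are inconsistent, pre-MCI is undefined, and the description of possible MCI sits in Section 12.0 rather than beside the criterion that relies on it. But this shows ambiguity and not conflict: *possible or pre-* can as easily be two near-equivalent qualifiers of one noun. That the Inclusion Criteria turn away intended participants depends on an intention the protocol does not state. The term in the Study Summary reads as shorthand, since the same table gives the population only as adults of 60 and over. The difference in setting, clinic or community, is explained in Sections 2.0 and 6.0, where recruitment widens to the community if the clinic cannot supply the sample.

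**Conclusion.** The concern does not hold as an eligibility contradiction. What remains is uneven terminology: three labels across six places, one of them undefined. The sections that control admission agree with each other, and following them gives a feasibility result for people with possible MCI, up to 60 of them, that can be reported as such. No screening decision, allocation or feasibility count under the written criteria depends on which label the descriptive sections use, and no statistical test is involved.

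This rests on two readings: that the Inclusion Criteria and Section 12.0 take precedence over descriptive text when people are admitted, and that nothing in the protocol makes pre-MCI separate from possible MCI. Using one label throughout would be tidier, but it is an editorial matter that analysts can handle by describing the enrolled sample as it was screened.
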